### **7.2.15 FSH Population Pharmacokinetics**

In addition to the sampling time points mentioned in section 7.2.14, blood samples will also be drawn at the oocyte retrieval visit for analysis of FSH.

Based on the serum FSH samples obtained during the trial, a population pharmacokinetic model will be developed to assess the pharmacokinetics of FE 999049 and confirm predictors for FSH

---

e AMH will also be included in the stimulation day 1 analyses.

concentration levels, such as body weight.

#### **7.2.16 Total Gonadotropin Dose and Number of Stimulation Days**

The start and end dates as well as daily dose of IMP will be recorded and used to calculate the total FE 999049 or GONAL-F dose administered and the number of stimulation days.

#### **7.2.17 Gonadotropin Dose Adjustments**

Investigator-requested decreases and increases of the gonadotropin dose will be captured during the stimulation period.

#### **7.2.18 Adverse Events**

Adverse events will be recorded from the signed informed consent for participation in the trial until the end-of-trial visit. For each adverse event the following parameters are recorded by the investigator on the Adverse Event Log: description of event, date and time of onset, intensity, causal relation to IMP, action taken to IMP, other actions taken, seriousness of the adverse event, date and time of outcome, and outcome. Furthermore, the pattern (e.g. the frequency, time of onset, intensity, seriousness and outcome) of the most frequent / relevant adverse events will be tabulated.

#### **7.2.19 Clinical Chemistry and Haematology Parameters**

The following clinical chemistry and haematology parameters will be analysed at a central laboratory:

CHEM-20: alanine transaminase, albumin, alkaline phosphatase, aspartate aminotransferase, bicarbonate, bilirubin direct, bilirubin total, blood urea nitrogen, calcium, chloride, cholesterol total, creatinine, gamma-glutamyl transpeptidase, glucose, lactate dehydrogenase, phosphorus, potassium, sodium, total protein, uric acid.

Complete Blood Count (CBC): red blood cells, red blood cell morphology, white blood cells, white blood cell morphology, haemoglobin, haematocrit, mean corpuscular volume, mean corpuscular haemoglobin, mean corpuscular haemoglobin concentration, platelets.

Blood samples will be drawn at screening, on stimulation day 1, end-of-stimulation and end-of-trial. The samples from the screening visit will be used for safety and eligibility evaluation of the subject before randomisation. The sample at stimulation day 1 (baseline) must be drawn before the first FE 999049 or GONAL-F injection. The investigator will review the laboratory results and evaluate and document whether the abnormal results are non-clinically or clinically significant. The Laboratory Report will be signed and dated by the investigator.

#### **7.2.20 Injection Site Reactions**

Every day throughout the stimulation period, the subjects will assess the local tolerability of subcutaneous injections of FE 999049 or GONAL-F at three time points relative to the daily administration: immediately after the injection, 30 minutes after the injection and 24 hours after the injection. The following injection site reactions will be assessed: redness, pain, itching, swelling

and bruising. The presence and intensity of each injection site reaction will be rated as one of the following: none, mild, moderate or severe.

The subject will record the assessments in a diary and the diary data will subsequently be transcribed to the e-CRF.

### 7.2.21 Anti-FSH Antibodies

Blood samples for assessment of anti-FSH antibodies in the individual subjects in the trial will be drawn pre-dosing and post-dosing:

- Screening [*note*: this sample is exclusively used as back-up sample for the anti-drug antibody assay development]
- Stimulation day 1, prior to dosing (baseline; pre-dosing sample)
- 5-10 days after the last FE 999049 or GONAL-F dose  
This may coincide with the transfer visit. Subjects not reaching transfer must be called in for this extra visit.
- 19-28 days after the last FE 999049 or GONAL-F dose  
This may coincide with the  $\beta$ hCG visit. In case of discontinuation before the  $\beta$ hCG visit, this assessment should be done at the end-of-trial visit scheduled 19-28 days after the last FE 999049 or GONAL-F dose.

Ferring has developed the following assays for evaluating the immunogenicity of FE 999049 or GONAL-F:

- Assay 1) A screening immunoassay, assessing the presence in serum of anti-FSH antibodies, using a parametric cut-point approach with a 5% false positive rate.
- Assay 2) A confirmatory immunoassay, confirming or disconfirming the specificity of any positive results in assay 1), using a parametric cut-point approach with a 0.1% false positive rate.
- Assay 3) A titre immunoassay determining the antibody response titre of any anti-FSH antibodies confirmed in assay 2).
- Assay 4) A cell-based assay qualitatively assessing the neutralising capacity of any anti-FSH antibodies confirmed in assay 2), using a parametric cut-point approach with a 1% false positive rate.
- Assay 5) A cell-based assay determining the neutralising antibody response titre of any positive result in assay 4).
- Assay 6) A confirmatory assay based on native FSH, in order to assess cross-reactivity with native FSH of any anti-FSH antibodies confirmed to be specific towards exogenous FSH in assay 2), using a parametric cut-point approach with a 0.1% false positive rate.

In subjects with a negative pre-dosing sample, a treatment-induced anti-FSH antibody response will be defined as any post-dosing sample being positive in the confirmatory assay; Assay 2).

In subjects with a positive pre-dosing sample, a treatment-induced anti-FSH antibody response will be defined as a statistically determined fold increase in titres from the pre-dosing assessment to a post-dosing assessment.f

All positive samples in the confirmatory Assay 2) will be further characterised for titre, neutralising capacity (qualitatively and titre) and cross-reactivity. A subject is defined to have treatment-induced anti-FSH antibodies with neutralising capacity if the subject has a positive outcome of assay 4) after IMP administration compared to pre-dose.

The proportion of subjects with treatment-induced anti-FSH antibodies and the proportion of subjects with treatment-induced anti-FSH antibodies with neutralising capacity are secondary endpoints.

Subjects with a treatment-induced anti-FSH antibody response (both with and without neutralising capacity) will be followed until the response becomes negative or has returned to pre-dosing level. These subjects will be called in for monthly assessments for a period of 3 months after the last post-dosing anti-FSH antibody sampling. If required, further assessments will be made quarterly, i.e. 6, 9 and 12 months after the last post-dosing anti-FSH antibody sampling. The assessments will be terminated when two consecutive assessments are negative or indicate that the pre-dosing level has been reached, with a maximum follow-up period of one year. The assessments will also be terminated if the subject commences a new treatment cycle with a gonadotropin preparation.

### **7.2.22 Immune-related Adverse Events**

All adverse events reported in the trial will be analysed to identify those that potentially are immune-related. To identify all possible cases, a broad-scope search on Standardised Medical Dictionary for Regulatory Activities (MedDRA) Queries (SMQs), including 'Hypersensitivity', 'Anaphylactic reactions', 'Angioedema' and 'Severe cutaneous adverse reactions' will be considered. Moreover, to identify the potential cases manifested by non-specific symptoms and not covered by these SMQs, other MedDRA PTs like 'Musculoskeletal pain', 'Asthenia', 'Pyrexia', 'Chills', 'Body temperature increased', 'Influenza like illness', 'Injection related reaction', 'Pre-syncope' and 'Syncope' will also be taken into account. Hypersensitivity reactions manifested by local symptoms will be identified using the MedDRA high level term (HLT) 'injection site reactions'. The SMQs may include very specific as well as less specific terms; hence a narrow-scope search on these SMQs will be carried out to identify those cases that are highly likely to represent an immune-related aetiology.

### **7.2.23 Cycle Cancellations due to an Adverse Event, including Immune-related Adverse Events, or due to Technical Malfunctions of the Administration Pen**

The reason for each cycle cancellation will be recorded. Among the options are adverse events, including immune-related adverse events, and technical malfunctions of the administration pen.

---

f The fold increase in titres will be determined by minimum significant ratio (MSR) experiments during assay validation. The clinical trial report will clearly state the MSR used in the data evaluation.

### **7.2.24 Late OHSS (including OHSS of Moderate/Severe Grade)**

Late OHSS is defined as OHSS with onset >9 days after triggering of final follicular maturation. Classification of grade is according to Golan's classification system (see section 8.3 for details) and all OHSS cases will be graded as mild, moderate or severe.

### **7.2.25 Multi-fetal Gestation, Biochemical Pregnancy, Spontaneous Abortion, Ectopic Pregnancy and Vanishing Twins**

Data related to multi-fetal gestation defined as a pregnancy with more than one fetus will be recorded. Furthermore, data related to the occurrence of biochemical pregnancy, spontaneous abortion, ectopic pregnancy (with and without medical/surgical interventions) and vanishing twins will also be recorded.

### **7.2.26 Pen Malfunction**

Incidences of technical malfunctions of the administration pen will be recorded.

## **7.3 Other Assessments**

### **7.3.1 Demographics**

Demographic information will be obtained during the screening period, including date of birth and confirmation of the subject's race and nationality. Mainland Chinese subjects must possess a Chinese identification card and have native Chinese parents.

### **7.3.2 Medical History**

Any relevant medical history will be recorded at screening. This includes diagnoses / symptoms and whether it is a past or ongoing occurrence.

### **7.3.3 Infertility History**

Information about the reasons of infertility will be obtained during the screening period. Duration of infertility will be recorded at the randomisation visit. This will also cover information about any previous treatment for infertility, including type of treatment and gonadotropin preparations used.

### **7.3.4 Menstrual History**

Information about the menstrual history (average cycle length) will be obtained during the screening period.

### **7.3.5 Reproductive History**

Information about the reproductive history will be obtained during the screening period. This will include number of clinical pregnancies, number of fetuses and outcome. Information on primary versus secondary infertility will be derived.

### **7.3.6 Smoking and Alcohol Habits**

Information about smoking and alcohol habits will be obtained during the screening period. Smoking will be categorised as 0, 1-5 or 6-10 cigarettes per day. Alcohol will be categorised as 0, 1-7 or 8-14 units per week.

### **7.3.7 Body Weight and Height**

Body weight will be measured at screening, stimulation day 1 and at end-of-trial. Body weight will be measured without shoes and overcoat and using a calibrated scale. The body weight at randomisation will be used for dose calculation in the FE 999049 group.

Height will only be measured at screening and will be used to calculate BMI.

### **7.3.8 Physical Examination**

A complete physical examination will be performed at screening and end-of-trial. Information will be recorded for general appearance, central and peripheral nervous system, head and neck (including ears, eyes, nose, mouth and throat), respiratory system, cardiovascular system, gastrointestinal system, lymphatic system, urinary system, musculoskeletal system and skin.

At screening, each category will be evaluated as normal, abnormal not clinically significant or abnormal clinically significant. Abnormal clinically significant findings at screening must be reported on the Medical History Log.

At end-of-trial, potential changes from screening to end-of-trial will be evaluated for each category. In case of changes, these will be evaluated as normal, abnormal not clinically significant or abnormal clinically significant. Abnormal clinically significant changes from screening to end-of-trial must be recorded as adverse events.

### **7.3.9 Gynaecological Examination**

A complete gynaecological examination will be performed at screening and end-of-trial. Information will be recorded for breast, external genitalia, vagina, cervix, uterus, ovaries and fallopian tubes.

At screening, each category will be evaluated as normal, abnormal not clinically significant or abnormal clinically significant. Abnormal clinically significant findings at screening must be reported as medical history or as reason for infertility on the Infertility History form, as applicable, and evaluated in accordance with inclusion criteria 8 and 9 (section 4.1.1).

At end-of-trial, potential changes from screening to end-of-trial will be evaluated for each category. In case of changes, these will be evaluated as normal, abnormal not clinically significant or

abnormal clinically significant. Abnormal clinically significant changes from screening to end-of-trial must be recorded as adverse events.

### **7.3.10 Endocrine Parameters at Screening**

At screening, the following panel of endocrine parameters will be evaluated (screening panel): AMH, TSH and prolactin. The sample will be analysed at a central laboratory.

The results of the screening panel must be available prior to randomisation. The investigator will review and evaluate the laboratory results (with the exception of AMH, which will not be made available to the investigator). The Laboratory Report will be signed and dated by the investigator.

The AMH samples collected at screening may be used for correlation analysis of Elecsys® AMH immunoassay results determined at provincial local laboratories versus the central laboratory.

### **7.3.11 Vital Signs**

Systolic and diastolic blood pressure as well as pulse will be measured at screening, stimulation day 1 and end-of-trial. All assessments of vital signs will be done while the subject is in supine position after resting for 3 minutes.

### **7.3.12 Ovarian Volume**

As part of the transvaginal ultrasounds performed at stimulation day 1 and end-of-stimulation, the size – length, width and depth (recorded in mm) – of each ovary is measured and used for subsequent calculation of ovarian volume.

### **7.3.13 Endometrial Status**

Transvaginal ultrasound of the uterus to assess the endometrial status will be conducted at all visits during the stimulation period. The endometrial status assessments consist of the following parameters: endometrial thickness, endometrial triple-layer structure and endometrial echogenicity pattern (*note*: the latter two are not assessed on stimulation day 1).

Endometrial thickness (composed of both layers of the endometrium) will be measured in the sagittal view of the uterus from the proximal and distal interfaces between the echogenic endometrium and the hypoechoic inner layer of the myometrium. Care should be taken not to include the hypoechoic subendometrial halo and to account for the presence of any fluid in the uterine cavity (not to be included in the endometrial thickness value). Endometrial thickness will be recorded in mm.

Endometrial triple-layer structure will be recorded as observed or not.

Endometrial echogenicity pattern will be recorded as hypoechoic, isoechoic, hyperechoic, or not possible to evaluate.

### **7.3.14 Embryo Transfer Procedure**

Any difficulty or eventuality (e.g. greater resistance is met, the procedure is time-consuming, there is a need to change to a harder catheter, uterine sounding or cervical dilation is carried out, or there is blood in any part of the catheter), during the transfer procedure will be noted.

### **7.3.15 Concomitant Medication**

The use of any concomitant medication within the last 3 months prior to informed consent for participation in the trial (except medication used in previous infertility treatment cycles) and throughout the trial will be recorded. Recording of concomitant medication will be performed at all visits. Any changes in concomitant medications or treatments must be recorded at each visit.

### **7.3.16 Drug Dispensing and Accountability**

For all medicinal products, dates of administration and dose administered will be recorded. Furthermore, time of administration will also be recorded for IMP, GnRH antagonist, hCG and GnRH agonist. Details on drug dispensing and accountability are provided in section 5.7.

### **7.3.17 End-of-trial Form**

An end-of-trial form must be filled in at the subject's last visit, irrespective of whether the subject completes the trial or not. Completion / discontinuation status will be recorded, as well as date and reason for discontinuation in case the subject did not complete the trial.

## **7.4 Assessments Related to Post-trial Information**

### **7.4.1 Pregnancy Follow-up**

For subjects with an ongoing pregnancy, information on the pregnancy period, including any relevant interventions performed and incidence of second or third trimester losses, as well as the pregnancy outcome, e.g. live birth, will be gathered. Further, neonatal health data will be collected at birth and at 4 weeks after birth for all children born. At birth, the data collected will include gender, birth weight and length, way of delivery, position of neonate and Apgar score as well as information on any congenital anomalies and admission to neonatal intensive care unit (NICU) or neonatal care unit (NCU). At 4 weeks after birth, the data collected will include any congenital anomalies, hospitalisations, death of neonate and any other relevant medical conditions. These follow-up data can be obtained from the subject, unless medical judgement is required.

These data will be reported separately.

## **7.5 Handling of Biological Samples**

A trial-specific laboratory manual will be provided to the participating sites, describing in detail how to handle, store and transport the biological samples (blood) in this trial. All biological samples will be analysed at central laboratories and will be maintained in storage after the end of the trial. Destruction will take place within 2 years after reporting of the trial or when methods /

results have been adequately validated. For all biological samples collected in the trial, it applies that analyses beyond those described in the protocol can only be performed after obtaining the required approvals. The processes related to handling of biological samples will be described in the informed consent documents, and biobank / data protection legislation including local legislation will be adhered to.

## 8 ADVERSE EVENTS

### 8.1 Adverse Event Definition

An adverse event is any untoward medical occurrence in a subject participating in a clinical trial. It includes:

- Any unfavourable and unintended sign, symptom or disease temporally associated with the use of the IMP, whether or not considered to be caused by the IMP.
- Adverse events commonly observed and adverse events anticipated based on the pharmacological effect of the IMP.
- Any laboratory abnormality, vital sign or finding from physical or gynaecological examination assessed as clinically significant by the investigator [*note*: pre-existing conditions diagnosed through assessments and examinations at the screening visit or during the screening period are not adverse events, but are recorded as medical history.]
- Accidental injuries, reasons for any change in medication (drug and/or dose), reasons for any medical, nursing or pharmacy consultation, or reasons for admission to hospital or surgical procedures.

All adverse events will be coded by Ferring Global Pharmacovigilance using MedDRA (the version effective at trial start).

### 8.2 Collection and Recording of Adverse Events

#### 8.2.1 Collection of Adverse Events

The investigator must monitor the condition of the subject throughout the trial from the time of obtaining informed consent until the end-of-trial visit.

The sources of adverse events cover:

- The subject's response to questions about her health (a standard non-leading question such as "How have you been feeling since your last visit?" is asked at each visit).
- Symptoms spontaneously reported by the subject.
- Investigations and examinations where the findings are assessed by the investigator to be clinically significant changes or abnormalities.
- Other information relating to the subject's health becoming known to the investigator (e.g. hospitalisation).

#### 8.2.2 Recording of Adverse Events

The investigator must record all adverse events in the Adverse Event Log provided in each subject's e-CRF with information about:

- Adverse event
- Date and time of onset

- Intensity
- Causal relationship to IMP
- Action taken to IMP
- Other action taken
- Date and time of outcome
- Outcome
- Seriousness

Each of the items in the Adverse Event Log is described in detail in the following sections.

### **Adverse Event**

Adverse events should be recorded as diagnoses, if available. If not, separate signs and symptoms should be recorded. One diagnosis / symptom should be entered per record.

If a subject suffers from the same adverse event more than once and the subject recovers in between the events, the adverse events should be recorded separately. If an adverse event changes in intensity, a worst-case approach should be used when recording the event, i.e. the highest intensity and the longest duration of the event.g

*Note:* A procedure is not an adverse event; the reason for conducting the procedure is. Hospitalisation is not an adverse event; the reason for hospitalisation is. Death is not an adverse event, but the cause of death is (an exception is sudden death of unknown cause, which is an adverse event).

### **Date and Time of Onset**

The date of onset is the date when the first sign(s) or symptom(s) were first noted. If the adverse event is an abnormal clinically significant laboratory test or outcome of an examination, the onset date is the date the sample was taken or the examination was performed.

---

g Exception: if an adverse event with onset before the first IMP administration (i.e. a pre-treatment adverse event) changes in intensity after the administration of the IMP, this must be recorded as two separate events. The initial adverse event should be recorded with outcome “not yet recovered” and the date and time of outcome is when the intensity changed. The second adverse event should be recorded with date and time of onset when the intensity changed.

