## **Intensity**

The intensity of an adverse event must be classified using the following 3-point scale:

- Mild: Awareness of signs or symptoms, but no disruption of usual activity.  
Moderate: Event sufficient to affect usual activity (disturbing).  
Severe: Inability to work or perform usual activities (unacceptable).

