### **Adverse Events**

#### *Adverse Events – General*

Adverse events will be coded using MedDRA. The version of MedDRA will be documented.

Adverse events are grouped according to start of IMP as follows:

- Pre-treatment adverse event, i.e. any adverse event occurring after signed informed consent and before start of IMP, or a pre-existing medical condition that worsens in intensity after signed informed consent but before start of IMP.
- Treatment-emergent adverse event, i.e. any adverse event occurring after start of IMP and before the end-of-trial visit, or a pre-treatment adverse event or pre-existing medical condition that worsens in intensity after start of IMP and before the end-of-trial visit.

Treatment-emergent adverse events will be presented in summary tables and listings. Pre-treatment adverse events will be presented in a listing only.

A treatment-emergent adverse event overview table will be prepared including the number of subjects reporting an adverse event, the percentage of subjects with an adverse event, and the number of events reported, for the following categories: all adverse events, severe adverse events, adverse reactions, adverse events leading to discontinuation, serious adverse events and deaths. An adverse reaction is an adverse event judged by the investigator to be related to IMP with a reasonable possibility.

Treatment-emergent adverse events will be tabulated by system organ class (SOC) alphabetically and preferred term (PT) in decreasing order of frequency. The following will be presented: number of subjects reporting an adverse event, the percentage of subjects with an adverse event, and the number of events reported.

Summary tables will be produced for the following: all adverse events, adverse events by causality (reasonable possibility / no reasonable possibility), adverse events leading to death, adverse events by intensity (mild / moderate / severe), adverse reactions by intensity (mild / moderate / severe), serious adverse events, adverse events leading to discontinuation, adverse events with an incidence of  $\geq 5\%$  in any treatment group, and non-serious adverse events with an incidence of  $\geq 5\%$  in any treatment group.

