#### **10.2 Adverse Events**

Adverse events will be coded using MedDRA. The version of MedDRA will be documented.

Adverse events are grouped according to start of IMP as follows:

- Pre-treatment adverse event, i.e. any adverse event occurring after signed informed consent and before start of IMP, or a pre-existing medical condition that worsens in intensity after signed informed consent but before start of IMP.
- Treatment-emergent adverse event, i.e. any adverse event occurring after start of IMP and before the end-of-trial visit, or a pre-treatment adverse event or pre-existing medical condition that worsens in intensity after start of IMP and before the end-of-trial visit.

If the timing of an AE cannot be established in relation to the administration of IMP, it will be considered as a treatment emergent AE.

In addition to the grouping of adverse events described in the protocol, adverse events will be categorised as 'other significant adverse events' and 'unexpected non-serious adverse drug reactions'. These events will be identified in a blinded review of the data before declaration of clean file and lock of database.

Treatment-emergent adverse events will be presented in summary tables and listings. Pre-treatment adverse events will be presented in listings only.

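### A pre-treatment adverse event that only partly improves after the first dose is, read literally, counted as treatment-emergent, although only worsening is meant to count

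*Protocol*

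**What the plan says.** Protocol 8.2.2 sets a general rule for an event whose intensity varies. It is kept as one record, and "a worst-case approach should be used when recording the event, i.e. the highest intensity and the longest duration of the event". The general onset rule in the same section is "The date of onset is the date when the first sign(s) or symptom(s) were first noted".

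Footnote g makes an exception for events that began before the first dose. If such an event "changes in intensity after the administration of the IMP, this must be recorded as two separate events". The first record is closed at the time of the change. For the second, "The second adverse event should be recorded with date and time of onset when the intensity changed".

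Protocol 9.7.3 and SAP 10.2 define treatment-emergent events in two limbs joined by 'or'. In the SAP, limb 1 is "any adverse event occurring after start of IMP and before the end-of-trial visit" and limb 2 begins "a pre-treatment adverse event or pre-existing medical condition that worsens in intensity after start of IMP". The protocol's limb 2 is the same: "a pre-treatment adverse event or pre-existing medical condition that worsens in intensity after start of IMP and before the end-of-trial visit".

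The class decides where an event is shown. Treatment-emergent events go into the summary tables and listings, whereas pre-treatment events are only listed.

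**The concern.** Footnote g is triggered by any change, but limb 2 admits a pre-treatment event only if it gets worse. By turning the continuation into a separate event with a post-dose onset, the footnote lets an improving event enter through limb 1, which sets no condition on direction.

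The outcome is the wrong way round. Take an event that arises after consent and is moderate at the first dose. If it eases to mild, the woman gains a treatment-emergent event. If it stays moderate, she does not.

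Frequency and intensity of adverse events is a secondary endpoint, and these tables are the main general safety display. Each extra record raises the event count. It raises the overall subject count only if the woman has no other treatment-emergent event. Each extra record also needs its own causality rating.

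**Working it through.** The documents state no figure for this point, so there is none to reproduce. The check traces records through the recording rule and then through the definition.

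**Inputs**
- Intensity scale (Protocol 8.2.2, Intensity): "The intensity of an adverse event must be classified using the following 3-point scale", namely mild, moderate and severe.
- Splitting rule: footnote g, mandatory and without direction.
- Limb 1: post-dose occurrence is enough.
- Limb 2: worsening is required.

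**Possible changes.** With three grades there are 3 × 2 = 6 ordered changes, 3 upward and 3 downward.

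| Grade at first dose → later grade | Split by footnote g | Second record meets limb 1 | Worsening (limb 2) | Literal result | Result limb 2 implies |
|---|---|---|---|---|---|
| mild → moderate | yes | yes | yes | treatment-emergent | treatment-emergent |
| mild → severe | yes | yes | yes | treatment-emergent | treatment-emergent |
| moderate → severe | yes | yes | yes | treatment-emergent | treatment-emergent |
| moderate → mild | yes | yes | no | treatment-emergent | pre-treatment |
| severe → moderate | yes | yes | no | treatment-emergent | pre-treatment |
| severe → mild | yes | yes | no | treatment-emergent | pre-treatment |
| no change | no | no second record | no | pre-treatment | pre-treatment |
| full recovery | no | no second record | no | pre-treatment | pre-treatment |

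Footnote g splits all 6 changes and limb 2 admits 3. The other 3 are the misclassified cases.

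**Is there a rule elsewhere that removes the second record?** I found none.
- The items of the Adverse Event Log in Protocol 8.2.2 include no link to a parent event.
- SAP 10.2 does not compare the intensities of the two records.
- Its only tie-break concerns events whose timing relative to IMP cannot be established, and it assigns them to the treatment-emergent class.

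**What narrows the effect**
- A mild event has no lower grade, so it cannot be affected.
- The second record is always mild or moderate, so the split cannot add to the severe category.
- Under Protocol 8.1, pre-existing conditions diagnosed at the screening visit or during the screening period are medical history and not adverse events. Under Protocol 7.3.2, relevant diagnoses and symptoms are recorded as medical history at screening. Footnote g does not apply to these.
- What remains is an adverse event that arose between consent and first dose, was moderate or severe at first dose, and then stepped down without resolving.

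**The case against.** The strongest reply is that no sentence says the second record is treatment-emergent. Limb 2 was written for exactly this kind of event, and footnote g itself describes the parent as a pre-treatment event. On that view the specific limb governs the general one. Otherwise the worsening condition would have little work left to do for recorded adverse events. The evident purpose of the footnote also points to worsening, because without it a post-dose deterioration would be absorbed into a record with a pre-dose onset.

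This stands in part. Counting the improved record is the literal reading, not an explicit instruction, and the wording looks like a drafting slip. But the limbs are alternatives, so meeting limb 1 is enough. The footnote calls the records separate events, and a programmer working from onset dates has no stated rule that would exclude the second one. The reading in which limb 2 governs needs a rule that has not been written.

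Three stronger readings are tempting, and the documents do not support them:

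- **A material percentage of women is affected.** The documents give neither the rate of adverse events ongoing at first dose nor the share that steps down a grade. Any percentage would be a product of two guesses.
- **Differences between arms are seriously diluted.** Suppose a share s of women in each arm independently gains a spurious event. A risk p becomes p + s(1 − p), so the risk difference is multiplied by (1 − s). With an assumed s of 2%, a 5.0-point difference becomes 5.0 × 0.98 = 4.9. With an assumed s of 4.5%, it becomes 5.0 × 0.955 ≈ 4.8. The loss is negligible. SAP 10.2 also plans tables of general adverse events without a test between arms.
- **Resolving symptoms will appear as adverse drug reactions.** An event that began before dosing and then eased fits the category of no reasonable possibility in Protocol 8.2.2. Worst-case imputation applies only where causality is missing.

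**Conclusion.** The mismatch between recording and counting rules is real and can be confirmed from the text. Taken literally, the plan moves partly improved pre-treatment events from the listings into the treatment-emergent tables, contrary to what limb 2 shows was meant.

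The point is minor. Only three kinds of grade change are affected, in a narrow group of events. The direction is a slight over-report of harm in both arms. The primary endpoint is untouched. Injection site reactions taken from the diary, OHSS classed by onset relative to triggering, and anti-FSH antibodies do not depend on this definition.

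The conclusion rests on two assumptions: that sites follow footnote g as written, and that limb 1 is programmed on the recorded onset. The view that the number affected is small is a judgement from the narrowing conditions, not a derived figure.

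**What to change.** Add to SAP 10.2, before the database is locked: *A continuation record of a pre-treatment adverse event (same term, onset equal to the outcome date/time of the pre-treatment record) is treatment-emergent only if its intensity is higher than that of the pre-treatment record; otherwise it is listed with the pre-treatment event.*

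No new data are needed. Footnote g gives the first record's outcome and the second record's onset the same date and time, so the pairs can be matched within subject. The matching should not rely on the outcome label, because the one named in footnote g is not among the outcome categories listed in Protocol 8.2.2.

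If the protocol is amended for other reasons, the trigger in footnote g should also be narrowed from a change in intensity to an increase in intensity. An improving event would then stay a single record with its pre-dose onset under the general rule. This edit needs an amendment under Protocol 12.1 and does not justify one alone. The SAP sentence costs one line of text and a short matching step in the programming.
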